#### **4.0 DEVICE INFORMATION**

Quotient ADHD system

The following devices have already been implanted in patients. We will only temporarily be changing the settings.

Activa PC 37601  
Activa SC 37602  
Activa SC 37603  
BS lead 3387 and 3389

Please see Investigators Device Brochures for more information.

#### **5.0 SELECTION AND WITHDRAWAL OF SUBJECTS**

Participants with idiopathic Parkinson's disease with motor fluctuations and/or dyskinesias that have received bilateral electrode implantation in the subthalamic nucleus are candidates for this study. Recruitment will take place during routine outpatient follow up clinic visits and by telephone or email, using a patient database from the deep brain stimulation case conference to identify suitable patients. Volunteers that are candidates for the study will be screened with neuropsychological assessment to exclude patients with dementia or clinical depression. For those patients that meet enrollment criteria and complete informed consent, testing will occur as a separately scheduled visit. Patients must be able to sit and participate for the duration of the testing period. Any condition in which the judgment of the investigator would prevent the subject from completion of the study will be excluded.

Inclusion Criteria:

1. Male or female patients who had previously undergone bilateral STN deep brain stimulation implantation
2. Age >18 years old
3. Stable medication regimen for at least 3 months.
4. Patient informed and able to give written consent
5. Able to comply with all testing, follow-ups and study appointments and protocols

Exclusion Criteria:

1. History of epilepsy or seizure
2. History of major substance abuse
3. Patients with baseline settings at less than 1.5 V will be excluded from the study

Subjects have the right to withdraw from the study at any time, for any reason, without jeopardizing their medical care

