## 3.0 STUDY DESIGN

In this single-center pilot study, we will investigate possible short-term neurocognitive changes induced by deep brain stimulation (DBS) in patients with Parkinson’s disease between the “on” and off” state. During the “on” phase, bilateral monopolar stimulation of the electrode contact associated with the ventral STN will be turned on; testing in the “on” state will be tested at both theta (5-10 Hz) and gamma (100-180 Hz) stimulation. In order to improve blinding to “on” versus “off” states and increase the uniformity of stimulation parameters, the intensity will be adjusted to 2.5 V for all patients. Patients with baseline settings at less than 1.5 V will be excluded from the study. During the “off” phase, both DBS electrodes will be turned off. Since turning the stimulation “on” vs “off” may induce motor effects that could influence testing performance, we will examine if the order in which settings are applied impacts the results of cognitive testing.

During a single outpatient visit, a baseline assessment (baseline stimulation parameters, including frequency, pulse width and voltage) of each neuropsychological task will first be performed in order to accommodate patients to the given task and reduce practice effect. Patients will then perform a battery of tests with the stimulator “on” at the theta frequency, “on” at the gamma frequency, and off; the sequence of these three settings will be changed for each patient in a single-blind fashion. Thus, patients will complete this battery of tasks a total of four times. Duration of testing will be approximately three hours.

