#### **6.0 STRATIFICATION/DESCRIPTIVE FACTORS/RANDOMIZATION SCHEME**

The order of stimulation parameters after baseline will be changed for each patient by moving the order by one step. E.g. patient 1: gamma, theta off; patient 2: theta, off, gamma; patient 3: off, gamma theta. The subject will not be told which setting is being used.

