#### **7.0 STUDY AGENT ADMINISTRATION OR INTERVENTION AND TOXICITY MANAGEMENT PLAN**

During the "on" phase, bilateral monopolar stimulation of the electrode contact associated with the ventral STN will be turned on; testing in the "on" state will be tested at both theta (5-10 Hz) and gamma (100-180 Hz) stimulation. In order to

improve blinding to “on” versus “off” states and increase the uniformity of stimulation parameters, the intensity will be adjusted to 2.5 V for all patients. During the “off” phase, both DBS electrodes will be turned off.

Parkinson’s disease patients routinely have their settings changed to optimize their therapy if they are not having adequate response to their current treatment, especially in their first few programming sessions. Patients also have a controller to turn it off and on. Stimulation is routinely turned off in clinic to check for symptoms, or by the patients, who have a controller. Many patients turn their stimulation off at night or for other reasons. The length of time (45 minutes) and adjustments that we are performing would only be for research. Theta stimulation is not routinely used clinically and would only be for research.

There are no risks of turning the stimulation off or lowering the frequency, but it is possible that during this they will not have the motor benefits of DBS (tremor, bradykinesia may return); however, once normal stimulation is turned back on this will resolve. Patients will be monitored during the testing and can stop participating at any point and we will return their stimulation settings back to baseline.

The CTSI Scientific Committee reviewed this study

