### 9.0 CLINICAL AND LABORATORY EVALUATIONS AND STUDY CALENDAR

Baseline (Session 1)	Session 2	Session 3	Session 4
RNGT (5 minutes)	RNGT (5 minutes)	RNGT (5 minutes)	RNGT (5 minutes)
Verbal Fluency (5 minutes)	Verbal Fluency (5 minutes)	Verbal Fluency (5 minutes)	Verbal Fluency (5 minutes)
D-KEFS CWIT (10 minutes)	D-KEFS CWIT (10 minutes)	D-KEFS CWIT (10 minutes)	D-KEFS CWIT (10 minutes)
Quotient Task (20 minutes)	Quotient Task (20 minutes)	Quotient Task (20 minutes)	Quotient Task (20 minutes)

(All during one day)

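### Medication state can shift between the stimulation settings being compared, because sessions are not tied to doses and dose times are not recorded; the expected cost is lost precision, not bias

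*Combined protocol and SAP*

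**What the plan says.** Section 5.0 describes candidates as patients with idiopathic Parkinson's disease "with motor fluctuations and/or dyskinesias that have received bilateral electrode implantation" in the subthalamic nucleus. The only inclusion or exclusion criterion about medication is "Stable medication regimen for at least 3 months".

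Section 3.0 puts a baseline battery and the three compared settings into one outpatient visit: "Thus, patients will complete this battery of tasks a total of four times", and "Duration of testing will be approximately three hours". The calendar in section 9.0 adds "All during one day". Section 7.0 gives the time per setting: "The length of time (45 minutes) and adjustments that we are performing would only be for research".

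On order, section 6.0 says: "The order of stimulation parameters after baseline will be changed for each patient by moving the order by one step". Section 3.0 plans to examine order effects, but the reason it gives is the motor effect of switching stimulation, not medication. It also plans movement data with stimulation on and off, to protect interpretation of the Quotient measures.

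Medications appear in section 3.0 only as an item taken from the chart. The analysis in section 13.0 is a within-subjects ANOVA per task, with no term for session position, medication state or time since dose. Nothing says whether patients are tested on or off medication, when the visit falls relative to a dose, whether doses may be taken during it, or that dose times are recorded.

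**The concern.** The trial's contrasts are all within patient and within one day. A criterion that holds the prescription steady for three months does not hold the patient's condition steady for three hours, and the plan recruits people whose motor condition fluctuates. Followed as written, one patient may be tested soon after a dose, another as a dose wears off, and a third may take a dose between two of the compared settings. A difference between two settings then carries whatever change in medication state fell between them.

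The protocol already accepts that motor state can affect test performance: that is its stated reason for looking at order. It guards against this for stimulation but leaves medication unmeasured. If dose times are not written down on the day, no later analysis can adjust for them or show how large the effect was. Both aims (stimulation on versus off, and theta versus gamma) depend on the same within-patient differences.

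**Working it through.** **1. The time window (the plan's own figure).** Task times in section 9.0 add to 5 + 5 + 10 + 20 = 40 minutes, so four batteries take 4 × 40 = 160 minutes of task time. At the 45 minutes of section 7.0, 4 × 45 = 180 minutes, which reproduces the stated three hours. The three compared sessions then start at about 45, 90 and 135 minutes. The first and third compared settings start 135 − 45 = 90 minutes apart.

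**2. What the rotation removes.** The sequences in section 6.0 are gamma–theta–off, theta–off–gamma and off–gamma–theta. Let every patient drift by the same amount b per session. By sequence, the drift enters each contrast as follows:

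- gamma − theta: −b, +2b, −b (sum 0)
- gamma − off: −2b, +b, +b (sum 0)
- theta − off: −b, −b, +2b (sum 0)

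With equal sequences (10 each at 30 patients), a common drift cancels from every group mean contrast. It still adds (1 + 4 + 1)b²/3 = 2b² to the variance of a paired difference unless session position is in the model.

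**3. What the rotation does not remove.** Suppose each patient has one of the three sessions, at random, shifted by d (in units of the tabled SD). A given pairwise difference is moved by +d with probability 1/3, by −d with probability 1/3, and otherwise not at all. The mean effect is 0 and the added variance is (2/3)d². Without the shift, the variance of the difference is 2(1 − r), where r is the within-patient correlation. So

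SD of difference = SD × √[2(1 − r) + (2/3)d²].

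**4. Illustration for verbal fluency.** Inputs from section 13.0: change 9.4, SD 17, 30 patients. Assumptions, because the documents give no values: d of 0.3, 0.5 or 0.8; r of 0.5, 0.7 or 0.8; two-sided 5% paired t test.

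Example at r = 0.5, d = 0.5: variance 1 + (2/3)(0.25) = 1.167. SD of difference = 17 × √1.167 = 18.4. Noncentrality = (9.4/18.4) × √30 = 2.80. Power is 0.77, against 0.83 with no shift.

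| r | No shift | d = 0.3 | d = 0.5 | d = 0.8 |
|---|---|---|---|---|
| 0.5 | 0.83 | 0.81 (+6%) | 0.77 (+17%) | 0.69 (+43%) |
| 0.7 | 0.97 | 0.95 (+10%) | 0.92 (+28%) | 0.82 (+71%) |
| 0.8 | nearly 1.00 | 0.99 (+15%) | 0.97 (+42%) | 0.90 (+107%) |

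Each cell gives power, with the rise in variance of the difference in brackets. The two must be read together: the largest variance rise (107%) leaves power at 0.90. At r = 0.5 and d = 0.5, the other powered rows go from 0.90 to 0.85 (RNGT) and from 0.82 to 0.76 (D-KEFS).

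**5. Dependence on the model.** If instead every session carries its own independent shift, with SD 0.3 or 0.5 of the tabled SD, then at r = 0.5 the SD of the difference is 17 × √(1 + 2 × 0.09) = 18.5 or 17 × √(1 + 2 × 0.25) = 20.8. Power is then 0.77 or 0.67.

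**6. Side check.** Section 13.0 states neither alpha nor power. A two-sided 5% paired t test at 80% power needs 23, 29 and 28 patients for the RNGT, D-KEFS and verbal fluency rows, against the stated 20, 26 and 29. The point here does not depend on those figures.

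**The case against.** A reader might infer that medication state does shift, and that this biases the comparison in favour of one setting. The documents support neither. They contain no dose times, so only a possible shift can be claimed. Section 5.0 names fluctuations and dyskinesias without calling them medication-related or saying that they persist after implantation. The rotation puts each setting in each position equally often. Swings unrelated to sequence therefore add noise and do not favour a setting. Bias would need unequal sequence groups or a drift that differs by sequence. A swing can distort one patient's own contrast, but the planned analysis is of the group.

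The step from motor state to cognitive score is also not documented. No passage says that medication wearing off moves these test scores, or by how much, so the shift sizes above have no anchor. If the tabled SDs, or the correlation assumed here, already reflect patients tested without control of dose timing, ordinary fluctuation is partly counted twice. And this is a pilot of 30 patients.

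These objections limit the certainty and the size of the point, and they stand. They do not remove it. The nearby safeguards do not cover the gap: the movement data serve only the Quotient and cannot tell a medication change from a stimulation change, and the order check addresses sequence, not dose timing.

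**Conclusion.** The concern holds as a risk to precision and interpretation. Medication state can differ between the settings compared within a patient, and the plan neither aligns visits to doses nor records what would be needed to adjust for it. Systematic bias is not expected while the three sequences stay balanced.

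The size is unknown. Under the one-session model, verbal fluency power falls below 0.80 only at r = 0.5 with a shift of 0.5 SD or more (0.77 and 0.69). At r = 0.7 or 0.8 it stays at 0.82 or above. The model with a shift in every session is harsher at r = 0.5. All of these rest on assumed shifts, assumed correlations and a two-sided 5% paired t test. The case for acting rests less on these figures than on the fact that dose times cost little to log on the day and, if left unrecorded, leave nothing to adjust with.

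**What to change.** In section 3.0, start each visit at a common interval after the patient's usual dose. The interval and the medication condition for testing are for the investigator to choose and state, with each patient's regimen unchanged. Log the clock time of each session start and of every dose taken on the visit day.

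In section 13.0, add session position to the within-subjects model. Where doses fall mid-visit or at different times, add time since last dose as a sensitivity analysis. It is not suited to the main model: once visits start at a common interval, it largely tracks session position unless a dose is taken during testing.

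Do not adjust for the patient's observed on, wearing-off or dyskinetic state. Section 7.0 says that tremor and bradykinesia may return when stimulation is off or its frequency is lowered. A state rated after the switch would therefore absorb part of the stimulation effect, and one rated before it would reflect the previous setting.

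The cost is less flexible visit times, two extra form fields, one model term and one sensitivity analysis. Aligning the start will not stop patients wearing off at different times, which is why the log is needed as well.

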#### **6.0 STRATIFICATION/DESCRIPTIVE FACTORS/RANDOMIZATION SCHEME**

The order of stimulation parameters after baseline will be changed for each patient by moving the order by one step. E.g. patient 1: gamma, theta off; patient 2: theta, off, gamma; patient 3: off, gamma theta. The subject will not be told which setting is being used.

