### 8.0 ASSESSMENT OF EFFICACY AND SAFETY

Patients will be monitored during the testing. We will ask the patient to inform us if they are feeling uncomfortable and want to stop participating or take a break. If patients want to stop participating, we will return the patients stimulation settings to baseline. Any adverse side effects will be reported to the IRB.

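### The one-step rotation uses only three of the six orders, so unequal carry-over can bias the setting contrasts and the promised order check could hardly show it

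*Combined protocol and SAP*

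**What the plan says.** Section 6.0 sets the allocation rule: "The order of stimulation parameters after baseline will be changed for each patient by moving the order by one step". It illustrates it with "patient 1: gamma, theta off; patient 2: theta, off, gamma; patient 3: off, gamma theta".

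Section 3.0 describes one visit. It begins with "a baseline assessment (baseline stimulation parameters, including frequency, pulse width and voltage) of each neuropsychological task will first be performed", followed by the three study settings, and adds: "Duration of testing will be approximately three hours". The calendar in section 9.0 gives 5 + 5 + 10 + 20 = 40 minutes of tests per session and notes "All during one day".

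On order effects, section 3.0 promises that "we will examine if the order in which settings are applied impacts the results of cognitive testing". Section 13.0 names non-parametric analysis and a within-subjects ANOVA, with no term for position, sequence or carry-over.

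The documents state no washout. Section 7.0 says of lost motor benefit that "once normal stimulation is turned back on this will resolve"; it gives no time course and does not address cognition. Section 8.0 lets a patient who is uncomfortable "want to stop participating or take a break".

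**The concern.** In a three-period crossover on one day, a setting's effect may persist into the next session. The rotation gives every setting the same predecessor whenever it is not first. A lingering gamma effect would therefore fall on theta and on no other study setting, and it would look like an effect of theta itself.

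Aim 2 rests on theta minus gamma, and Aim 1 on gamma minus off. The direction of any bias is unknown. Section 1.0 reports better RNGT performance with high-frequency stimulation; if that lingered, the bias would favour theta, which is the trial's hypothesis. Section 1.0 also reports a decline in verbal fluency; if gamma lowered that score and the effect lingered, the bias would run against theta. The RNGT is the first task after each change, so later tasks may carry less.

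The plan itself raises order as a threat, and the promised order check is its only safeguard against carry-over. The question is whether these three orders let that check work.

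**Working it through.** The plan gives no carry-over figure to reproduce. Its projected sample sizes (20, 26 and 29) are not in dispute here.

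**1. Predecessors.** The orders are gamma-theta-off, theta-off-gamma and off-gamma-theta. With n = 30 (section 13.0) there are 10 patients per order.

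| Setting | Follows baseline | Follows gamma | Follows theta | Follows off |
|---|---|---|---|---|
| Theta | 10 | 20 | – | 0 |
| Off | 10 | 0 | 20 | – |
| Gamma | 10 | 0 | 0 | 20 |

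With all six orders, five patients each, every cell is 10.

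**2. Bias.** Let Lg, Lt and Lo be the residual effects of gamma, theta and off on the next session, and Lb that of baseline. Under the rotation the theta mean picks up (2/3)Lg + (1/3)Lb and the gamma mean picks up (2/3)Lo + (1/3)Lb. The baseline term cancels. The other contrasts follow in the same way.

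| Contrast | Rotation | Six orders, unadjusted |
|---|---|---|
| Theta minus gamma | (2/3)(Lg − Lo) | (1/3)(Lg − Lt) |
| Gamma minus off | (2/3)(Lo − Lt) | (1/3)(Lo − Lg) |
| Theta minus off | (2/3)(Lg − Lt) | (1/3)(Lo − Lt) |

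Equal residual effects cancel. If one setting alone lingers, the rotation biases two of the three contrasts.

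**3. Precision.** This step uses least squares with patient, position and setting effects, with and without first-order carry-over. Variances are in units of the within-patient residual variance.

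| Quantity | Rotation | Six orders |
|---|---|---|
| Setting contrast, unadjusted | 0.0667 | 0.0667 |
| Setting contrast, adjusted for carry-over | 0.3333 | 0.0833 |
| Efficiency after adjustment | 0.0667/0.3333 = 20% | 0.0667/0.0833 = 80% |
| Lg − Lo | 0.60 | 0.15 |

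Steps 1 to 3 need no assumption about SD or carry-over size.

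**4. Illustration: only gamma lingers.** The assumptions are:
- n = 30, with the paired-difference SD equal to the tabled SD (within-patient correlation 0.5, residual variance 0.5);
- no carry-over from off, and theta truly equal to gamma;
- two-sided 5% pairwise t-tests on 56 df, although the plan names no pairwise test.

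The standard error is √(0.5 × 0.0667) = 0.183 SD. For the RNGT the effect is 8.6/14 = 0.614 SD; for verbal fluency it is 9.4/17 = 0.553 SD. The RNGT bias is (2/3) × carry-over.

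| Carry-over as share of effect | RNGT bias | False positives, RNGT, rotation | RNGT, six orders unadjusted | Verbal fluency, rotation |
|---|---|---|---|---|
| 10% | 0.04 SD (0.57 points) | 5.6% | 5.1% | 5.4% |
| 25% | 0.10 SD (1.43) | 8.5% | 5.9% | 7.9% |
| 50% | 0.20 SD (2.87) | 19.7% | 8.5% | 16.8% |

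Simulated signed-rank tests give similar rates under the rotation: 5.6, 8.2 and 17.9% for the RNGT.

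**5. Illustration: only theta lingers**, in the direction of the planned 0.553 SD effect. Under the rotation, power for gamma minus off falls from 84.5% to 79.3, 69.9 and 51.0% at the same three levels. Six orders leave it at 84.5%.

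**6. The order check.** With carry-over terms (54 df), the 95% confidence half-width for a setting contrast is 2.005 × √(0.5 × 0.3333) = 0.82 SD under the rotation and 2.005 × √(0.5 × 0.0833) = 0.41 SD with six orders. Power for 0.553 SD is 26.5% against 75.8%. Power to detect a difference Lg − Lo of half that effect is 7.9% against 16.8%; for a difference as large as the whole effect it is 16.8% against 50.9%.

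**The case against.** - **No carry-over is shown.** The documents report none on any cognitive task. This stands: the size of the harm is unknown, and at 10% carry-over it is negligible. The bias factors and the weakness of the check are properties of the design and hold regardless.
- **The correlation of 0.5 is assumed.** This also stands. Over correlations of 0.3 to 0.8, the 19.7% becomes 15.4 to 41.4%, adjusted rotation power of 26.5% becomes 20 to 56%, and adjusted six-order power of 75.8% becomes 61 to 99%. The ranking of the designs does not change.
- **Timing.** Section 7.0 mentions 45 minutes. Read as time per setting, 4 × 45 = 180 minutes matches the three-hour visit and leaves 45 − 40 = 5 minutes beyond each battery. That is not a stated washout, and nothing fixes the gap between settings.
- **The rotation is a recognised design for a pilot.** It balances position, so additive practice and fatigue effects cancel, and the baseline run reduces practice effects. That is a real merit, but it does not address carry-over.
- **Six orders are not better for every contrast.** If only gamma lingers at 50% of 0.553 SD, unadjusted power for gamma minus off falls from 84.5% to 69.9%, where the rotation is unbiased. If only theta lingers at 50%, theta minus gamma is biased by −0.09 SD, again where the rotation is unbiased. If gamma and theta have opposite residual effects and theta's is the larger, six orders are worse for theta minus gamma. All this stands. Yet the squared biases summed over the three contrasts are always (1/3)²/(2/3)² = one quarter of the rotation's, because both designs involve the same three differences.

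**Conclusion.** The point holds as a low-cost design improvement, not as a demonstrated error. Three of six orders are used, and each unadjusted contrast carries two thirds of a difference in residual effects. The order check the plan relies on would work at 20% efficiency where 80% is available. These statements need only the allocation rule and a first-order carry-over model.

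Whether results would be distorted depends on carry-over that the documents do not quantify. The false-positive and power figures are illustrations under the assumptions listed. Six orders do not make carry-over easy to detect; they make its estimate four times as precise (variance 0.15 against 0.60) and make adjusted contrasts usable.

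**What to change.** **Section 6.0.** Replace the rotation with all six orders of gamma, theta and off, five patients per order at n = 30. Assign them from a random list generated before enrolment in blocks of six.

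**Section 13.0.** Include setting and position in the within-patient model for each task. Define the order check promised in section 3.0 as a prespecified sensitivity analysis: a linear model that adds first-order carry-over terms for the preceding study setting. Report its adjusted contrasts with 95% confidence intervals whether or not carry-over is significant. State how this sits beside the non-parametric analysis also named there.

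**Why a sensitivity analysis.** Adjustment costs precision: 75.8% against 84.5% power at 0.553 SD. For theta minus gamma, the adjusted six-order analysis beats the unadjusted rotation on mean squared error only when the bias exceeds √(0.5 × (1/12 − 1/15)) = 0.091 SD. That means a difference Lg − Lo above 0.091/(2/3) = 0.14 SD, about 25% of the effect (16 to 29% over correlations of 0.8 to 0.3).

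**Cost.** One paragraph in section 6.0, a few sentences in section 13.0 and a list. Patients, sessions, settings, visit length and unadjusted precision are unchanged. The change must precede enrolment, because analysis cannot supply predecessor pairs that never occurred. No washout length is proposed, since the documents give no basis for one.

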### 13.0 STATISTICAL CONSIDERATIONS

Based upon our power analyses, our sample sizes for each of the tasks range from 20-29 patients. Therefore, we will enroll 30 patients to detect significant differences in cognitive function for the first phase of the study.

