## Power analyses

Study	Projected Sample Size	Mean Result ± SD	Absolute Change (Percent Change)
RNGT	20	43±14	+8.6 (20%)
Delis Kaplan Executive Function	26	9.1±3.3	±1.8 (20%)
Verbal Fluency (preliminary data)	29	47±17	+9.4 (20%)
Quotient	Exploratory		

Non-parametric data analysis will be performed for each of the tasks, including RNGT, D-KEFS CWIT and the Quotient tasks. Each task will be analyzed using within-subjects ANOVA.

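### The order of settings follows a fixed, foreseeable rotation with no random or concealed assignment, which exposes the promised order check to selection and the setting contrasts only under further conditions

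*Combined protocol and SAP*

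**What the plan says.** Section 6.0, whose composite title includes a randomization scheme, gives one allocation rule: "The order of stimulation parameters after baseline will be changed for each patient by moving the order by one step". Its example is "patient 1: gamma, theta off; patient 2: theta, off, gamma; patient 3: off, gamma theta". Section 3.0 adds only that "the sequence of these three settings will be changed for each patient in a single-blind fashion". On masking, section 6.0 says "The subject will not be told which setting is being used"; nothing is said about whoever books the visit, programs the stimulator or scores the tests.

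Section 5.0 says that, after eligibility and consent, "testing will occur as a separately scheduled visit". No section says whether the patient number is given at consent, at booking or on the test day.

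Section 3.0 promises an order check: "we will examine if the order in which settings are applied impacts the results of cognitive testing". No model is given for it. Section 13.0 sets the sample size: "we will enroll 30 patients to detect significant differences in cognitive function". The analysis is stated as "Each task will be analyzed using within-subjects ANOVA", with no term named for order or session position.

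**The concern.** The order is a fixed function of patient number, so anyone who knows one patient's order knows the next. If a patient's number is settled only when the visit is booked, a booking decision could determine who receives which order. This need not be improper. Section 7.0 notes that motor benefit may be lost with stimulation off or at lower frequency, and staff might in good faith prefer a certain order for a frailer patient.

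Two results could be affected. One is the order check, which relies on the three order groups being comparable. The other is the set of contrasts between gamma, theta and off, if the groups differ in a way that within-patient comparison does not remove.

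**Working it through.** The plan states no figure on this point, so there is none to reproduce. The check asks what selection into orders can and cannot distort.

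**Inputs.** Three orders from section 6.0; 30 patients from section 13.0, hence 30/3 = 10 per order if the rotation is completed; planned differences and SDs from the power table in section 13.0. Session trends and the simulation SDs are assumptions.

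**Step 1: position balance.** Position of each setting among the three study sessions:

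| Order | Gamma | Theta | Off | Gamma minus off gap |
|---|---|---|---|---|
| gamma-theta-off | 1 | 2 | 3 | 1 − 3 = −2 |
| theta-off-gamma | 3 | 1 | 2 | 3 − 2 = +1 |
| off-gamma-theta | 2 | 3 | 1 | 2 − 1 = +1 |

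Each setting is first, second and third in 10 patients, and the gaps sum to zero. A patient's overall level drops out of every setting contrast, and a session trend common to all patients also cancels.

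**Step 2: unequal trends.** Let b1, b2, b3 be the mean change per session in the three orders, in the order of the table. With equal group sizes:

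- bias in gamma minus off = (−2·b1 + b2 + b3)/3
- bias in theta minus gamma = (b1 − 2·b2 + b3)/3

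Assume a scale where higher is better, and an extra decline of s SD per session in the gamma-theta-off group only, so b1 = b − s and b2 = b3 = b. Gamma minus off then shifts by (−2b + 2s + 2b)/3 = 2s/3 SD. For s = 0.1 that is 0.067 SD. For s = 0 it is zero.

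**Step 3: scale.** Planned effects in SD units are 8.6/14 = 0.614 (RNGT), 1.8/3.3 = 0.545 (D-KEFS) and 9.4/17 = 0.553 (verbal fluency). The shift at s = 0.1 is 0.067/0.614 = 11% to 0.067/0.545 = 12% of these.

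**Step 4: simulation.** 30 patients, 10 per order, no true setting effect, 4,000 runs. Assumed SDs: patient 12, residual 7, individual slope 3 points per session. The order check compared each patient's mean over the three settings across orders at the 5% level.

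| Assignment to the three orders | Mean bias, theta minus gamma | Type I error, theta vs gamma | False order effect |
|---|---|---|---|
| Random | 0.03 points | 5% | 5% |
| Extreme sorting by level | 0.01 points | 4.6% | about 100% |
| Extreme sorting by slope | −3.2 points | 36% | 14% |

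The sorted rows are worst cases under assumed SDs. They show which results are vulnerable, not the expected size. Sorting by level leaves the setting contrast untouched but destroys the order check, because each patient is tested in one order only and comparing orders means comparing different patients.

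**The case against.** The strongest reply is that every patient receives all three settings and the rotation balances position exactly. Bias in a setting contrast would require patients to be steered by their individual trend or their response to a setting. Nothing shows that staff would have that information before the visit. This stands, and it confines the concern for the setting contrasts to a conditional one.

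The order check is not helpless either. Each patient completes the battery at baseline settings first, so the data exist to adjust for differences in level, although the plan states no such adjustment. With 10 patients per order, randomisation would not guarantee comparable groups; it would remove systematic selection.

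Three stronger readings are tempting but unsupported:

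- *Staff know the order before choosing who fills a slot.* The documents do not say so. If numbers are given at consent, the order is fixed before booking and the choice of slot changes nothing. The text leaves this open.
- *Coded result sheets reveal the setting.* That needs study codes that follow the rotation. Section 12.0 says only that results are de-identified with a key.
- *The bias could exceed a third of the planned effect.* At s = 0.3 the shift is 0.20 SD, or 0.20/0.545 = 37% of the smallest planned effect. But this assumes one group declines 2 × 0.3 = 0.6 SD more than the others from first to third setting, about as much as the planned effects themselves.

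Nor does the section title amount to a broken promise: the text beneath it never claims that the order is drawn at random.

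**Conclusion.** The point holds in limited form. The order is foreseeable by rule, and the documents contain no random or concealed assignment and no statement that would stop booking from influencing it. The order check is directly exposed to selection of patients into orders.

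The setting contrasts are protected against differences in overall level. They are biased only if the order groups differ in practice or fatigue trend, or in response to a setting. The illustrative size is 2s/3 SD, or 0.07 SD at s = 0.1, where s is an assumption and not a figure from the documents. The documents neither show steering nor rule it out, and without it the expected bias is zero. This is a low-priority improvement, worth making because it costs so little.

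**What to change.** In section 6.0, replace the one-step rule with a computer-generated random list that gives 10 patients to each order. Use a full shuffle of all 30 assignments, or blocks of varying, undisclosed size. Avoid fixed blocks of three: someone who knows the earlier orders could guess the next with probability 1/3, then 1/2, then 1, an average of 61%.

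Keep the list concealed, in numbered sealed envelopes or a locked file. The person programming the stimulator should open each entry only after that patient's Session 1 baseline battery is complete. By then the patient is already under test, so booking cannot depend on the order.

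The cost is a few lines of text, a one-time list and minor list or envelope handling. No patients, visits or staff are added, and position balance is kept at 10 per order. The change does not address the separate matter that only three of the six possible orders are used.
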